4 STUDY OBJECTIVES

4.1 Overall Objective

The overall objective of this study is to evaluate the efficacy of the use of the OCS in ACL reconstruction.

4.2 Primary Objective

The study seeks primarily to determine the effect of the use of the OCS-autograft fixation construct on femoral bone tunnel widening compared to the traditional ACL-reconstruction technique using a hamstring autograft.

4.3 Secondary Objectives

Secondary objectives are to assess patient subjective measures of knee function and objective measures of knee stability of the interventional treatment compared to the control treatment. Also the success of return to pre-injury activity level will be assessed. Additionally OCS-bone integration will be investigated.

4.4 Safety Objectives

Safety will be evaluated by the occurrence, frequency and severity of intra- and postoperative complications.

5 STUDY OUTCOMES

5.1 Primary Outcome

The primary outcome variable of this study is the relative change of the CT evaluated femoral bone tunnel volume from baseline to follow-up at 12 months.

As the primary objective of the use of the OCS is to reduce tunnel widening by promoting bony ingrowth into the bone tunnel, the relative change of bone tunnel volume over time is an appropriate measure to quantitatively assess this effect. Assessing relative changes as opposed to absolute values negates the potential for bias by different tunnel drill sizes used in the two treatment arms potentially influencing the absolute ossification/de-ossification. In quantifying bone tunnel size, CT measurements provide substantially more reliable means than plain radiography or magnetic resonance imaging [50, 68].

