3.1.1 Bone Tunnel Widening following ACL-Reconstruction

BTW is a well-documented phenomenon following ACL-reconstruction [16, 38-40]. In studies using hamstring grafts, it has occurred in 25-100% in the femoral tunnel and in 29-100% in the tibial tunnel [41-45]. Although it may not affect the clinical outcome in terms of an increase in laxity or failure rates [46], it severely complicates revision surgery [40]. Etiological factors for tunnel widening probably are of mechanical, as well as of biological nature. Mechanical factors include motion of the graft within the bone tunnel, stress shielding and improper graft placement. Synovial fluid propagation into the bone tunnel and increased cytokine levels inducing osteolysis are believed to be biological factors leading to this phenomenon [40]. Bone tunnel widening can be assessed on plain radiograph [47], MRI [48] and CT with CT being the most accurate [49, 50]. In an attempt to reduce tunnel widening following ACL-reconstruction, osteoconductive materials have been used with promising results. The use of a poly-L-lactic acid (PLLA)-HA blended interference screw reduced tunnel widening compared to plain PLLA interference screws at an average follow-up of 30.9 months and 26.5 months, respectively (29.9 vs. 46% BTW) [46]. Similarly, Barth et al. [51] showed a statistically significant reduction of BTW using a poly (L-lactide-co-D,L-lactide) (PLDLLA)-HA/β-TCP composite screw compared to the polymer-only screw in the tibia, but not in the femur. PLLA/HA composite screws also outperformed metal interference screws for graft fixation in ACL-reconstruction in terms of BTW in a study conducted by Lind et al. [52]. Resorption of polymer-bioceramic interference screws however, is generally slow [53]. High mechanical loads during insertion do not allow the use of highly porous materials for interference screws. In the current application, the osteoconductive scaffold does not take primary fixation function. This allows the use of highly porous material.

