3.3.2 Autograft Scaffolds for ACL-Graft Fixation

Kim et al. [56] prospectively reviewed 81 patients who had undergone ACL-reconstruction with an Achilles tendon allograft using a bioabsorbable interference screw (group I) or an autogenous bone plug harvested from the tibial bone tunnel (group P) for tibial graft fixation. Patients and outcome-assessors were blinded to group assignment. After an average follow-up of 7.5 years, complication rate in group P was significantly less frequent than in group I (6 vs. 14) and tunnel widening, assessed as cross-sectional area on MRI, averaged 15% in group P and 38% in group I ($p = 0.017$). No significant changes for patient subjective outcome scores

and stability were detected. The authors deemed the use of autograft bone plugs for graft-fixation a reasonable option for ACL-reconstruction with Achilles tendon allograft.

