8.3 Bone Tunnels

The harvested unsutured tendon-graft must measure between 8 and 8.5 mm in diameter at the end to be inserted into the femoral bone tunnel for subject inclusion (see chapter 7.1.2). Enlacing the OCS increases the graft diameter by 1 mm (Determined experimentally).

Accordingly, the overdrilled socket of the femoral bone tunnel has the following diameter depending on the subject's group assignment:

- Intervention group: 9 - 9.5 mm
- Control group: 8 – 8.5 mm

The tibial bone tunnel is drilled at a diameter of 8 ± 1 mm as applicable.

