8.4 Surgical Technique

The surgical technique under study uses a semitendinosus tendon autograft (combined with gracilis tendon if applicable) harvested from the index knee or the contralateral knee according to the standard in-house technique. The pes anserinus is visualized through a three centimeter incision anteromedially at the proximal tibia. The semitendinosus tendon is harvested with a tendon stripper and length and thickness is measured. For the intraarticular procedure, standard medial and lateral parapatellar arthroscopy portals are used. After overdrilling with a 4.5 mm drill, the final femoral graft tunnel is created by a cannulated drill. Afterwards the tibial tunnel is prepared by using a drillguide (Karl Storz, Tuttlingen, Germany) targeted at the center of the tibial ACL footprint. The tendon graft is inserted first into the femoral bone tunnel through the medial portal. In the femoral tunnel the graft is secured using a flipping device on the cortical bone (Flipptack, KarlStorz, Tuttlingen, Germany). Tibial graft-fixation is achieved using an interference screw (Megafix, Karl Storz, Tuttlingen, Germany) proximally, and a small plate (Endotack, Karl Storz, Tuttlingen, Germany) covering the bone tunnel distally.

The table below shows a schematic of the surgical techniques for graft fixation under study and the material in use.

Control Intervention	Experimental Intervention

1) Femoral cortical fixation: Flipptack (Karl Storz) 2) Femoral Graft suspension: Ethibond 6 (Ethicon Inc.) Suture bone tunnel; diameter: 4.5 mm 3) Cannulated bone tunnel; diameter: 8 – 8.5 mm Length: 27 mm 4) Tendon graft 5) Resorbable interference screw fixation (Megafix, Karl Storz) 6) Tibial bone tunnel; Diameter: 8 – 8.5 mm Tibial Graft suspension: Fibre Wire 2 (Ethicon Inc.) and Ethibond 6 7) Tibial cortical fixation: Endotack (Karl Storz)
	
1) Femoral cortical fixation: Flipptack (Karl Storz) 2) Femoral Graft suspension: Ethibond 6 (Ethicon Inc.) Suture bone tunnel; diameter: 4.5 mm 3) Cannulated bone tunnel; diameter: 9 – 9.5 mm Length: 27 mm 4) Tendon graft 5) Resorbable interference screw fixation (Megafix, Karl Storz) 6) Tibial bone tunnel; Diameter: 8 – 8.5 mm Tibial Graft suspension: Fibre Wire 2 (Ethicon Inc.) and Ethibond 6 7) Tibial cortical fixation: Endotack (Karl Storz) Black Arrow: Medical device under study enlaced into tendon graft.

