11.4.2.1 Confounder-Controlled Analysis

Additionally to the analysis described above in a secondary analysis, group differences in relative change of bone tunnel volume from baseline to follow-up 2 and from baseline to follow-up 3 are assessed in an analysis of covariance (ANCOVA)-model, controlling for confounding factors. The preliminary model contains the following confounding factors:

- Patient sex [89]
- Patient age [89]
- Preinjury Tegner activity score
- Associated bone/meniscus/cartilage-injury (Present/Not Present)

In a univariate analysis each factor is tested for association with the dependent variable (relative change of bone tunnel volume). All factors with association $p < 0.2$ are then included in a preliminary ANCOVA. A stepwise modelling approach is then used where variables with association $p > 0.05$ are excluded. At each exclusion, the model is computed again. The order of exclusion of all factors not associated significantly with the dependent variable is opposite to the list shown above (i.e. from bottom to top) [90].

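### Relative change removes the drill-size difference between arms only if widening is proportional to diameter, and no planned tunnel analysis would show whether it is

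*Combined protocol and SAP*

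**What the plan says.** Section 5.1 makes the relative change in CT femoral tunnel volume from baseline to 12 months the primary outcome. It acknowledges that the arms are drilled to different sizes and sets the matter aside: "Assessing relative changes as opposed to absolute values negates the potential for bias by different tunnel drill sizes used in the two treatment arms".

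Section 8.3 gives the reason for the difference: "Enlacing the OCS increases the graft diameter by 1 mm (Determined experimentally". The femoral socket is therefore 8–8.5 mm in control and 9–9.5 mm in intervention. The table in 8.4 repeats this for the intervention arm ("Cannulated bone tunnel; diameter: 9 – 9.5 mm Length: 27 mm") and gives control the same length. The two diameter ranges do not overlap.

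All planned tunnel-size comparisons use relative change:
- the primary and Visit 4 analyses (11.4.2);
- the ANCOVA, which models "group differences in relative change of bone tunnel volume from baseline to follow-up 2" and to follow-up 3 (11.4.2.1);
- the femur–tibia comparison (5.3.3, 11.4.3.1);
- radiographic width (11.4.4);
- the interim analysis, run in the same way as the full analysis (11.4.5).

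Femoral tunnel diameter is recorded at surgery (9.2.4.3) but enters no analysis.

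**The concern.** A ratio to baseline is free of baseline size only when the change scales with baseline size. If the tunnel wall instead recedes by a similar distance in mm whatever the drill, a wider socket shows a smaller percentage change for the same biological process. Socket size is fixed by arm, so this would appear as a treatment difference in the confirmatory test. The planned secondary and supportive analyses share the same scale, so their agreement with the primary result would not be evidence against it. Section 5.1 presents as settled a geometric assumption that the plan never tests.

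**Working it through.** **Plan's own figure.** For a difference of 20 points, SD 25.175, two-sided α 0.05 and power 0.8 (11.2), n = 2 × [25.175 × (1.960 + 0.842)/20]² = 24.9, so 25 per group. Then 25/0.9 = 27.8, so 28 per group and N = 56. This agrees with the plan. The standard error of the difference is 25.175 × √(2/25) = 7.1 points.

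**Inputs.** Mid-range diameters are 8.25 mm (control) and 9.25 mm (intervention), with a 27 mm cylinder (8.3, 8.4). V = π/4 × D² × 27 gives 1,443 and 1,814 mm³, a ratio of 1.257. The protocol does not state the 12-month femoral widening to be expected, so control widening r is an assumption. I borrow 15% and 38% from 3.3.2 ("tunnel widening, assessed as cross-sectional area on MRI, averaged 15% in group P and 38% in group I") and about 30% and 46% from 3.1.1 ("respectively (29.9 vs. 46% BTW"). None is a 12-month femoral CT figure. All four are read as area, although 3.1.1 does not state the metric.

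**Three widening models, no device effect in any.**
- Proportional to diameter: both arms show r, so the gap is 0.
- Equal wall recession (same diameter gain w): w = 8.25 × (√(1+r) − 1), and intervention shows ((9.25+w)/9.25)² − 1.
- Equal volume gain: intervention shows r × (8.25/9.25)² = 0.795r.

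Rejection is from the noncentral t distribution with 25 per arm, df 48, two-sided 0.05.

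| Control r | w (mm) | Equal recession: intervention | Gap (points) | Rejection | Equal volume: intervention | Gap (points) | Rejection |
|---|---|---|---|---|---|---|---|
| 15% | 0.60 | 13.3% | 1.7 | 5.6% | 11.9% | 3.1 | 7.1% |
| 30% | 1.16 | 26.6% | 3.4 | 7.6% | 23.9% | 6.1 | 13.5% |
| 38% | 1.44 | 33.6% | 4.4 | 9.3% | 30.2% | 7.8 | 18.8% |
| 46% | 1.72 | 40.6% | 5.4 | 11.5% | 36.6% | 9.4 | 25.4% |

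All gaps favour the device.

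**Sensitivity of these figures.**
- If the 46% is a diameter figure, w = 0.46 × 8.25 = 3.80 mm. The volumes then rise by 113.2% and 98.9%, a gap of 14.3 points with about 50% rejection.
- If control narrows by 10/20/30%, equal recession gives 1.1/2.1/3.0 points against the device.
- If the mask includes an unchanged 4.5 mm suture tunnel of length L, relative change is 27[(D+w)² − D²]/(27D² + 4.5²L). At w = 1 mm the gap falls from 2.9 points (L = 0) to 2.2 (L = 10 mm) and 1.7 (L = 20 mm). L is assumed, because the documents do not give it.

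**Could a planned analysis reveal it?** Radiographic width under equal recession differs by w/8.25 − w/9.25, or 0.8–2.3 points, in the same direction. The ANCOVA has no diameter or baseline-volume term. Adding diameter would not repair this, because arm largely determines it. Simulated diameters spread over the permitted ranges give a variance inflation of about 5 to 14, and power for 20 points falls to about 0.23–0.11. The femur–tibia comparison is relative, uses one arm only, and mixes socket size with the scaffold and the bone site.

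**Behaviour of a mm-scale analysis.** Under equal recession it is unbiased. Under proportional widening it is biased against the device by (9.25 − 8.25) × (√(1+r) − 1) = 0.07–0.21 mm. With a delta-method SD of D × 0.25175/(2√(1+r)), pooled over arms at 1.03–0.91 mm, false rejection is 5.7–12.4%. Under equal volume gain it favours the device by 0.06/0.11/0.14/0.16 mm, the same direction as the relative scale.

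**The case against.** The strongest reply is that the larger socket belongs to the technique. The device requires it, and the objectives compare a fixation construct with the traditional technique, so any socket effect is part of the contrast. That is a legitimate estimand, but 5.1 does not adopt it. It says the drill-size influence is removed, so the sentence needs changing on either reading.

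It is also fair that relative change is a better primary scale than absolute volume, which differs by about 371 mm³ (1,814 − 1,443) at baseline from the drill alone. That stands, and the choice of primary scale is not disputed.

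A reader might infer that the trial is biased in favour of the device. The documents do not support this. Equal recession and equal volume gain are as unproven as proportionality, and the direction depends on whether tunnels widen or narrow. A reader might equally infer that the bias is small because it lies below one standard error. That holds in the equal-recession columns with 46% read as area, but not for equal volume gain at 38% or 46%, nor for 46% read as a diameter.

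A reader might also suspect that scaffold voxels in the intensity-based mask add a further bias. Section 9.2.1 refers the segmentation procedure to a work instruction that was not available for review, and the scaffold's volume is not stated, so no finding can rest on it.

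**Conclusion.** The concern holds in a limited form. The unconditional claim in 5.1 does not follow from the design in 8.3 and 8.4, and no planned tunnel comparison could expose its failure. With no device effect, the spurious difference on the primary outcome is:
- zero under proportional widening;
- 1.7–5.4 points under equal wall recession (8–27% of the 20-point target);
- 3.1–9.4 points under equal volume gain (15–47%);
- about 14 points under equal recession if the 46% is a diameter figure.

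These figures assume mid-range cylinders, the planned SD, 25 per arm and borrowed widening rates. They show that the assumption matters; they do not bound the bias or establish its direction. The point warrants correction before analysis but does not undermine the choice of primary outcome.

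**What to change.** 1. **Section 5.1.** Replace *negates* with a conditional statement: relative change is free of drill-size bias only if widening is proportional to diameter. Otherwise the contrast includes the effect of the larger socket as part of the device technique.

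2. **Section 11.4.2.** Keep relative change as primary. Add one pre-specified sensitivity analysis from the same masks: change from baseline to 12 months in equivalent tunnel diameter, √(4V/(πL)), with L the baseline socket length held fixed at all visits. Report the group difference in mm with its 95% CI.

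3. **Reading of the two results.** State that the relative scale is unbiased under proportional widening and the mm scale under equal wall recession. Agreement covers those two models only. It does not show independence from the widening model, since equal volume gain pushes both scales the same way. Judge agreement by estimates and intervals, not by shared non-significance.

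The cost is wording and one extra analysis of volumes already planned. The downside is the mm scale's own bias of 0.07–0.21 mm against the device if widening is proportional, so it should remain a sensitivity result.

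A separate minor point: on the tibial side, 8.3 says "The tibial bone tunnel is drilled at a diameter of 8 ± 1 mm as applicable" and the table in 8.4 says "Tibial bone tunnel; Diameter: 8 – 8.5 mm". The two passages must be reconciled.

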5.2 Secondary Outcomes

The secondary endpoints aim to assess the clinical outcome of the two treatment groups. These clinical outcome measures can be divided into two domains: Patient subjective knee function and objective measures of knee stability.

5.2.1 Patient Subjective Knee Function

Patient subjective knee function is assessed using the International Knee Documentation Committee (IKDC) Subjective Knee Evaluation Form (SKEF) and the Lysholm Knee Scoring Scale (LKSS) measured at baseline visit (surgery) and at each follow-up visit.

5.2.1.1 IKDC Subjective Knee Evaluation Form

IKDC SKEF is designed to detect improvement or deterioration in symptoms, function and sports activities due to knee impairment for patients with a variety of knee conditions including ligament injuries. It is a patient-completed questionnaire available in multiple languages including German with an ordinal scoring system ranging from 0 (highest level of symptoms or lowest level of function) to 100 (no limitation with daily or sporting activities and the absence of symptoms) [69].

5.2.1.2 Lysholm Knee Scoring Scale

LKSS is designed to evaluate outcomes of knee ligament surgery, particularly symptoms of instability [70]. It has an ordinal scoring system ranging from 0 to 100 (No symptoms or disability) [71]. A validated German version will be used [72].

5.2.2 Objective Measures of Knee Stability

Anterior laxity is evaluated using the KT-1000 Arthrometer Test and the Lachman Test. Rotational stability is assessed using the Pivot Shift Test.

5.2.2.1 KT-1000 Arthrometer Test

The KT-1000 Arthrometer Test measures anterior displacement of the tibial plateau on the femur at a specific force. Its output variable is defined as the difference in full millimeters between the tibial displacement of the ACL reconstructed knee and the normal contralateral side [73].

5.2.2.2 Lachman Test

The Lachman test measures anterior displacement conducted manually by the clinician. It is graded as the difference from the normal contralateral side as 0 (<3 mm), 1 (3 to 5 mm), or 2 (>5 mm) [74].

5.2.2.3 Pivot Shift Test

The pivot shift test assesses the combined tibio-femoral rotation and anterior tibial translation. The pathologic motion elicited is graded as a glide (grade 1), clunk (grade 2), or gross clunk with locking (grade 3). A normal finding is graded as zero. The grade of the pivot shift has been shown to correlate with patient-reported functional instability and clinical outcomes [75]. The outcome measure is calculated from the difference between affected (repaired) and intact knee.

5.2.2.4 Tegner activity scale

The Tegner activity scale (TAS) is used to measure the change in physical activity from pre-injury to follow-up. It was designed to complement the functional outcome of the LKSS. Patient's activity is scored on a scale with 11 levels from level 0 (on sick leave/disability) to level 10 (participation in competitive sports such as soccer at a national or international elite level) [71]. Evaluated will be the difference in score from pre-injury (assessed at baseline visit) to follow-up.

5.3 Other Outcomes of Interest

5.3.1 Patient History

Patient history will be assessed using an adapted version of the IKDC SKEF (German version). Assessed will be:

- Date of injury
- Affected knee
- Activity of injury
- Mechanism of injury

5.3.2 OCS-Bone Integration

For a quantitative analysis of OCS-bone integration, the mineral density profile along a predefined line will be examined. A slice showing the central portion of the OCS in the axial plane will be selected. A straight line of 2 cm length will be drawn perpendicular to the long axis of the OCS using image analysis software (Mimics). The CT-values along this line will be recorded and evaluated in the following way. Since the CT-values change according to the bone mineral density, the profile along the line will have a minimum at the interface of the tunnel wall and the OCS and a maximum on the OCS. The difference in Hounsfield units from the cancellous bone in the tunnel wall and the OCS-bone interface will be used as a measure for the degree of osseous integration of the implant [24].

5.3.3 Intra-Patient Comparison of Ossification

The intervention group will be additionally assessed in an intra-patient comparison model [51]. Using the available CT data, the tibial bone tunnel volume will be calculated using the same method as for the femoral bone tunnel volume described below. The relative change of the two parameters will be compared.

5.3.4 Plain Radiography assessed Bone Tunnel Widening

BTW will additionally be assessed on plain radiograph. Standard posteroanterior radiographs of the knee in full extension will be used [76]. Bone tunnel width will be assessed at the widest part of the femoral bone tunnel. Assessed will be the relative change in femoral bone tunnel width.

5.4 Safety Outcomes

Any occurrence of intra-operative complications will be recorded on the eCRF. Post-operative (serious) adverse events will be recorded at each follow-up visit.

6 STUDY DESIGN AND COURSE OF STUDY

6.1 General study design and justification of design

The present study is designed as a randomized patient-blinded equally sized two-group parallel design superiority trial using an active comparator. ACL-reconstruction using the in-house standard of care will be compared to the method under investigation. In a two staged randomization, a total of 56 patients are assigned to either of the two treatment groups.

6.1.1 Time Frame of the Study

Currently, no precise time frame for the occurrence of BTW has been defined [41]. Chen et al. [77] investigated the incidence of BTW following ACL-reconstruction using hamstring tendon in 58 patients at 1, 2, 3, 6, 12 and 24 months postoperatively. BTW was found to mainly occur during 3 to 6 months after surgery with no change in bone tunnel volume between 12 and 24 months postoperatively. Similarly, Jo et al. [78] concluded, BTW to be maximal within the first 9 months following surgery using patellar tendon grafts. For the current trial, BTW-assessment using CT-scanning 4.5 and 12 months after surgery seems therefore reasonable. The need of correlating BTW with long-term clinical results has also been pointed out [79].

